8.1.2 Secondary study parameters/endpoints

- completion of 40 min upright bicycling bout at FATMAX (yes/no; if no, #minutes)
- completion of 5 min supine bicycling bout at FATMAX in scanner (yes/no; if no, #minutes)
- subjective fatigue and muscle ache score after each exercise bout (scale 0-10) and 24 hours after exercise
- blood levels of 3-OH butyrate, acetoacetate, acylcarnitines, glucose, lactate and pH prior to and post-exercise.
- optional: muscle levels of glycogen, lactate, 3-OH butyrate, and (very) long (C18-C14) to medium (C12-C8) to short chain (C6-C2) acetyl-carnitines prior to and immediately post-exercise (on a patient-voluntary basis)

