The effect has been attributed to enhanced muscle mitochondrial function in addition to glycogen sparing. Here, we will investigate if acute NK in adolescent and adult symptomatic VLCAD deficient patients can boost muscle mitochondrial function in vivo. If so, a rational basis will have been established for therapeutic use in this metabolic myopathy. This study will include patients from the age of 16 years that could benefit from NK as well. Since rhabdomyolysis often has an onset in adolescence, confirmation of our hypothesis would lead to therapeutic use in that age group as well. Moreover, older patients often suffer from severe exercise intolerance and loss of muscle function due to earlier episodes of rhabdomyolysis, leaving most of them unable to complete our study protocol. Due to the rarity of the disease and earlier argumentation, it's vital to include adolescent subjects to reach sufficient power in this study. As such, this study constitutes a vital first step towards possible validation of an effective treatment for patients with VLCADD that may improve the quality of life including an active lifestyle with overall health benefits.

Objective: To test if acute NK boosts muscle mitochondrial function in vivo in patients with VLCADD in order to establish a rational basis for therapeutic use in this disorder. A secondary objective is to gather data to test the working hypothesis that the positive effect of acute NK on muscle mitochondrial function results from enhanced substrate supply to the tricyclic acid (TCA) cycle.

Study design: randomised, blinded, placebo controlled, 2-way cross over trial.

Study population: Six Patients with VLCADD between 16 and 65 years of age, seen for evaluation in the VLCADD expertise centre of the UMC Utrecht.

Intervention (if applicable): Oral intake of nutritional drinks; prolonged moderate-intensity exercise on bicycle ergometer; in vivo Magnetic Resonance Spectroscopy; muscle microbiopsy; venipuncture.

Main study parameters/endpoints:

- Whole body:
 - Physical performance during a 45 bicycle exercise test at individual FATMAX workload (typically of the order of 40%MVO₂). Specifically:
 - completion of 40 min upright exercise bout at FATMAX workload (yes/no; if no, #minutes)
 - completion of 5 min in-magnet exercise bout at FATMAX workload (yes/no; if no, #minutes)
 - subjective fatigue and muscle ache score after each exercise bout (scale 0-10) and 24 hours after session (telephone consultation)

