1st biopsy: 20 min after oral drink; 2nd biopsy: immediately following end of exercise bout 1. objective: metabolomic profiling of the state of the energy metabolic network in muscle and mapping of individual phenotypic muscle properties (fiber type, mitochondrial density, capillary density). Biopsies will be obtained from the m. vastus lateralis of the left leg. Hereto, a preparatory superficial incision of the skin and fascii will be made under local sedation and bandaged, allowing fast and reproducible biopsy sampling prior to and immediately following exercise bout 1 below.

- 40 min upright bicycling exercise at FATMAX outside MR scanner (exercise bout 1)

Blood samples are collected every 10 minutes.

- microbiopsy from the quadriceps muscle (optional)

Biopsy will be obtained from the m. vastus lateralis of the left leg (see above).

- 5 min supine bicycling exercise at 50% MVO_2 inside MR scanner (exercise bout 2)

*serial in vivo ^{31}P MR spectra will be recorded non-invasively from the m. vastus lateralis of the right leg as previously (protocols **12-211/K** (VLCAD; UMC Utrecht); **NL41313.042.12** (MCAD; UMG) to determine energy and proton balance in the muscle during exercise and the kinetics of metabolic recovery following exercise. A blood sample will be taken after the subject has exited the scanner room. Final blood samples including on-site analysis of CK levels are taken up to 3 hr post-session III to monitor any rhabdomyolytic event.*

- 24 hours after session II and III, co-investigator [name] will call each subject to evaluate subjective fatigue and muscle complaints after the subject left the test facility.

Time between study sessions I and II will be at least 7 days; time between study sessions II and III will be 7 days. For session I, patients will be asked to abstain from food 3 hrs prior to the test. For sessions II and III, participants will be asked to keep a 'food diary' for the week prior to the test in order to monitor the caloric intake and macronutrient content of each participant. For sessions II and III, patients will travel to Groningen the evening prior to the study and will be housed in a hotel across the street from UMCG. Patients are able to take a

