3. STUDY DESIGN

This is a randomised, blinded, placebo controlled, two-way cross over trial. Patients with VLCADD will be recruited by the VLCADD Expertise Center at UMC Utrecht. Nutritional ketosis will be compared to a placebo, delivered as an isocaloric drink before exercise. An individualised, standardised bicycle exercise protocol will be completed by each participant with collection of blood metabolites, respired gases, and subjective ratings of fatigue and muscle complaints. In addition in vivo ³¹P MR Spectroscopic recordings will be made from the quadriceps muscle before (resting), during and post-exercise. An optional muscle biopsy will be obtained from the quadriceps before and after exercise.

Patients will be asked to participate in three study sessions:

session I (site: nearest Academic Medical Center, Pediatric test ward).

- standard maximal cardiopulmonary exercise test (CPET; bicycle ergometry with indirect calorimetry)
objective: determination of VO_{2max} in order to set the desired exercise workload of maximal individual rate of fat oxidation (FATMAX; typically ~40% MVO_2) in sessions II and III below.
- venipuncture
objective: measure rise in blood lactate and creatine kinase (CK) levels in response to CPET

sessions II and III (site: Neuroimaging Magnetic Resonance Center UMC Groningen).

- venipuncture + canulation
objective: prepare subject for serial (every 10 min) blood sampling for off-site metabolic profiling
- oral intake of nutritional drink A or B (ketone and placebo drinks, respectively)
Each subject will receive both drinks over the course of the trial in a blinded fashion – i.e., if drink A in session II, then drink B in session III, and vice versa.
- microbiopsy from the quadriceps muscle (optional)
*1st biopsy: 20 min after oral drink; 2nd biopsy: immediately following end of exercise bout.
objective: metabolomic profiling of the state of the energy metabolic network in muscle and mapping of individual phenotypic muscle properties (fiber type, mitochondrial density, capillary density). Biopsies will be obtained from the m. vastus lateralis of the left leg. Hereto, a preparatory superficial incision of the skin and fascii will be made under local sedation and bandaged, allowing fast and reproducible biopsy sampling prior to and immediately following exercise bout 1 below.*

- 40 min upright bicycling exercise at FATMAX outside MR scanner (exercise bout 1)

Blood samples are collected every 10 minutes.

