Subjects state subjective fatigue and muscle ache following exercise bout.

- microbiopsy from the quadriceps muscle (optional)

Biopsies will be obtained from the m. vastus lateralis of the left leg (see above).

- 5 min supine bicycling exercise at FATMAX inside MR scanner (exercise bout 2)

*serial in vivo 31P MR spectra will be recorded non-invasively from the m. vastus lateralis of the right leg as previously (protocols **12-211/K** (VLCAD; UMC Utrecht); **NL41313.042.12** (MCAD; UMG) to determine energy and proton balance in the muscle during exercise and the kinetics of metabolic recovery following exercise. Subjective fatigue and muscle ache scores and a blood sample will be taken after the subject has exited the scanner room. Final blood samples including on-site analysis of CK levels are taken up to 3 hr post-session III to monitor any rhabdomyolytic event.*

- 24 hours after session II and III, co-investigator [name] will call each subject to evaluate subjective fatigue and muscle complaints after the subject left the test facility.

Time interval between study sessions I and II will be at least 7 days; between study sessions II and III: 7 days. The night prior to sessions II and III, patients will be housed in close vicinity to the UMCG. Patients will be instructed to take a late evening snack or meal according to their individual record of maximal fasting duration, given a start time of the study at 08:00 am the following day. Patients will be allowed a light breakfast according their normal diet before they will receive the caloric drive before the test. The breakfast will be the same for session II and III.

The total duration of the first session will be around 45 minutes, with 30 minutes of preparation and 8-12 minutes of cycling (exact time length dependent on the maximal endurance of the participant). The total duration of the second and third session will be around 5 hours including 45 minutes of preparation, 45-60 minutes of bicycling for the submaximal endurance exercise test and 3 hours of post-exercise resting where after the last blood and urine sample will be collected. During this 3 hour period, participants will be asked to fill out a HAES diary and can watch a DVD to pass time.

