Blood samples of 1-2 ml will be drawn via a 3-way tap from a 22 G venous canula (for subject comfort) inserted into a forearm vein at the start of each study visit. Blood samples

for free fatty acids, glucose and other assays will be taken and stored on ice, subsequently centrifuged, and stored at -80 until further processing. Up to 7 samples will be taken from the canula (~15 ml of blood total): #1 and #2 at baseline (in duplo), #3-5 during exercise (every 10 min), #6 after 40 minutes of moderate-intensity exercise, and #7 after the final MRS-analysis when the participant has recovered from exercise.

Muscle biopsy:

Participants are given the option at the start of the trial of undergoing muscle biopsy. If the patient has given informed consent to muscle biopsy, samples will be taken before and after exercise testing protocol during one or both study visits (2 samples/run; maximal of four biopsies for the complete study). 0.25 gm. of muscle tissue will be collected using percutaneous needle biopsies from the lower third of the Vastus Lateralis muscle with a biopsy gun (Bard Monopty, Bard Biopsy Systems, USA; a sterile standard biopsy technique (SOP). Muscle biopsy will be obtained from new incisions under local anaesthesia. Tissue samples will be frozen immediately in liquid nitrogen and stored at -80 °C until further analysis. Assays include glycogen and the metabolites of the glycolytic, TCA cycles. If sufficient tissue is available, enzymatic activity of mitochondrial and cytosol proteins, muscle fibre types, amino acids, and fat stores will also be determined.

Storage of tissue samples

All samples will be frozen immediately and stored at -80°C in the laboratory for Liver, Digestive and Metabolic diseases of the department of Paediatrics at UMCG.

31P MRS

MR data gathering will be performed using a 3.0 T whole-body MR-scanner (Intera; Philips Medical Systems, Best, The Netherlands). Subjects are introduced to the scanner and exercise apparatus and instructed. MRS data gathering will be performed with a surface coil wrapped over the quadriceps muscle. Conventional anatomical MRI scans will be acquired for positioning and scanner preparation. 31P MR spectra will be acquired serially to measure dynamics in intramuscular PCr, ATP, Pi, and pH using standard 31P-MRS protocols.

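### The muscle ache score is not recorded by leg, so in biopsy volunteers it mixes left-thigh biopsy pain or numbness with exercise ache

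*Protocol*

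**What the plan says.** The ache endpoint in section 8.1.2 is "subjective fatigue and muscle ache score after each exercise bout (scale 0-10) and 24 hours after exercise". The summary lists the same ratings among its whole-body measures, with the 24-hour score taken by telephone. Section 3 says of bout 1, "Subjects state subjective fatigue and muscle ache following exercise bout", and of bout 2, "Subjective fatigue and muscle ache scores and a blood sample will be taken after the subject has exited the scanner room". None of these places names a leg or tells the patient to leave out pain at a biopsy site.

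Biopsy is voluntary. On site, section 3 says "Biopsies will be obtained from the m. vastus lateralis of the left leg". On timing, the summary says "1st biopsy: 20 min after oral drink; 2nd biopsy: immediately following end of exercise bout 1". Section 8.3 adds "Muscle biopsy will be obtained from new incisions under local anaesthesia", and lets a volunteer be sampled at one of the two study visits or at both, with two samples per visit and at most four in all.

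For spectroscopy the legs are kept apart: "serial in vivo 31P MR spectra will be recorded non-invasively from the m. vastus lateralis of the right leg as previously" (section 3).

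**The concern.** The ache score is there to show whether the ketone drink changes the ache that exercise causes. In a volunteer, a muscle that works during cycling is incised and sampled around the first bout. Soreness from that can raise the score, and local anaesthesia can lower it. The protocol protects the MRS data from this by using the other leg, but gives the ache score no such protection.

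Ache is one of the few endpoints that the patient feels, and there are only six patients, so one or two affected patients can matter. If the two sources are not separated when the question is asked, they cannot be separated afterwards.

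**Working it through.** The protocol gives no ache data and no power figure for this endpoint, so there is no stated number to reproduce. The check is the order of events, followed by arithmetic under stated assumptions.

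**Order of events in a biopsied session** (summary, sections 3 and 8.3)

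- First biopsy: 20 minutes after the drink, before bout 1.
- Rating after bout 1: follows the first biopsy. Section 3 lists it ahead of the second biopsy, but that biopsy is to be taken immediately after the bout and no order between the two is stated.
- Rating after bout 2: taken on leaving the scanner room, so after both biopsies.
- Rating at 24 hours: after both biopsies.

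Each patient gives 2 sessions × 3 ratings = 6 ache scores. In a biopsied session all three are exposed.

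**Biopsy at one visit only**

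Let biopsy add *b* points, assumed 1 to 3. Let *k* be the net number of patients biopsied at one visit only, under the same drink. The shift in the mean within-patient drink difference is *b* × *k* / 6.

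- *k* = 1: 1/6 = 0.17 to 3/6 = 0.50 points
- *k* = 2: 2/6 = 0.33 to 6/6 = 1.0 points
- *k* = 3: 3/6 = 0.5 to 9/6 = 1.5 points

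With one or three such volunteers, balance over the drinks is impossible. With two, and the biopsied visit random with respect to drink, the chance of balance is 2 × 0.5² = 0.50, so imbalance also has probability 0.50.

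**Biopsy at both visits**

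If *b* is the same at both visits, it cancels in the within-patient difference and the shift is 0. What remains is visit-to-visit variation in soreness. Its effect was simulated with these assumed inputs:

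- 0-10 scores, rounded and clipped; patient mean 3 (SD 1.5)
- drink effects of ±0.5, so a true difference of 1 point; session noise SD 0.7
- soreness mean 2 (SD 1.5), not below zero, added to the exercise ache

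| Between-visit correlation of soreness | SD of the drink difference | Chance that a patient's difference points the wrong way |
|---|---|---|
| No biopsy | 1.05 | 7% |
| 0 (independent) | 2.06 to 2.19 | 24 to 25% |
| 0.7 | about 1.4 to 1.5 | about 15 to 16% |
| 0.9 | about 1.2 | about 10% |

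The ranges reflect two ways of keeping soreness at or above zero. The mean difference stays near 0.98 in every additive case, so there is noise but no bias. If patients instead report only the worse of the two pains, with independent soreness, the mean difference falls from 0.97 to between 0.64 and 0.67 and the wrong-direction chance is about 17%.

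**The planned test**

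Section 10.2 names the Mann-Whitney test, which is unpaired. There, even a constant biopsy effect at both visits adds spread between patients. If 3 of 6 patients are biopsied, the added SD is *b* × √(0.5 × 0.5), or 0.5 to 1.5 points. A paired comparison would remove it.

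**The case against.** The strongest reply is about scope. Biopsy is optional, so the problem may touch few patients or none. The endpoint is secondary in section 8.1.2, no power is claimed for it, and the main MRS endpoints come from the right leg. In a cross-over, a volunteer biopsied at both visits acts as his or her own control. All of this stands, and it limits the weight of the point.

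A second reply is that a rating instruction or case report form, not shown here, may tell patients to rate exercise ache and ignore the wound. That could help with pain clearly felt at the site. It would not deal with numbness or diffuse soreness of the same thigh.

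A third reply is that the summary treats ache as a whole-body measure, so replacing it with a right-leg score for everyone would discard ache felt elsewhere. That is fair, and it is why the right-leg score need not displace the overall score.

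A reader might also infer more than the documents support:

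- That there is only one ache score per patient. There are six; what is missing is a split by leg.
- That biopsy biases the drink comparison in general. A constant effect cancels when both visits are biopsied; bias arises mainly when only one visit is.
- That a quarter of volunteers would show a difference in the wrong direction. That needs soreness to be independent between visits. The same procedure in the same muscle a week later may well be correlated, and the figure then falls towards 10%.

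**Conclusion.** The point holds as a flaw in how a secondary endpoint is measured. In biopsy volunteers, every ache score in a biopsied session can mix biopsy pain or numbness with exercise ache. The more serious route is biopsy at one visit only: 0.17 to 0.50 points in the six-patient mean per such patient, if biopsy adds 1 to 3 points. With biopsy at both visits the cost is mainly noise: a wrong-direction chance of about 10 to 25%, against 7% without biopsy, under additive soreness and correlations from 0.9 down to 0.

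The size of the biopsy effect, the drink effect and the correlation are all assumptions, and the number of volunteers is unknown. Even the direction is uncertain, because anaesthesia could lower the score. The MRS endpoints are not affected. The change is worth making because it is cheap and because analysis cannot repair the data later.

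**What to change.** In sections 8.1.2 and 3:

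- Record muscle ache separately for the right and the left leg after each bout and at the 24-hour call.
- State that the bout 1 rating is taken before the second biopsy.
- Record for each session whether a biopsy was done.
- Prespecify a drink comparison of ache on the right leg, which is never biopsied, at least beside the overall score. Report the left-leg score descriptively.

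The cost is one extra 0-10 question per rating, with no added visit or procedure. The downside is that ache felt only in the left leg, or elsewhere in the body, does not count in the right-leg analysis; keeping the overall score alongside it covers that loss.

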8.2 Randomisation, blinding and treatment allocation

Patients will be handed an unlabeled caloric drink (placebo and ketone ester drink) prior to the endurance exercise bout in each of the two study sessions at UMCG. All patients will receive both drinks over the course of the study. [name], who will

conduct the studies at UMCG together with PI [name], will plan, randomize and record the order of placebo and ketone ester administration to the patients. [name], who will analyze all MRS data, will not have, nor seek access to, these records thus ensuring blinded MRS data analysis.

8.3 Study procedures

The study is introduced to the patient by co-investigator [name], MD, of the VLCADD expertise center in Utrecht in correspondence with their individual metabolic paediatrician/internist. The study will be announced during the 'patient information day' that's annually held by the the IcFAO expertise centre and by electronic newsletter to which most VLCADD patients or their caretakers are subscribed. Eligible patients will receive an information letter about the study. After a two week consideration period co-investigator [name] will send a reminder letter to subjects who did not respond to the inquiry. This letter will repeat the invitation to participate in the study. If after one more week the subject fails to reply, it is assumed that the subject is not interested and he or she will not be contacted any further. If the subject is interested and has given informed consent, the patient is included in the study, and the subject will be checked for the inclusion- and exclusion criteria The investigator informs the subject about final inclusion, or possible exclusion of the study on basis of the criteria.

Session I: Determination of the VO₂max (CPET) and FATMAX.

Participants are asked to cycle at maximal speed on an ergometric bicycle on a functional test ward at the nearest UMC location (AMC, UMC Utrecht or UMC Groningen). Prior to this session they will be asked to complete a HAES questionnaire containing questions on exercise frequency and the presence of physical complaints during or after exercise.

Sessions II and III.

In the week prior to testing, participants will be asked to keep a 'food diary' for the week prior to the test in order to monitor the caloric intake and macronutrient content of each participant. For sessions II and III, patients will travel to Groningen the evening prior to the study and will be housed in a hotel across the street from UMCG. Patients will be instructed to take a late evening snack or meal in correspondence with their individual record of maximal fasting duration, given a start time of the study at 08:00 am the following day. Patients will be allowed the same light breakfast according their normal diet before they will receive the caloric drive before the test. The breakfast will be the same for session II and III.

Venipuncture and blood sampling:

Blood samples of 1-2 ml will be drawn via a 3-way tap from a 22 G venous canula (for subject comfort) inserted into a forearm vein at the start of each study visit. Blood samples

for free fatty acids, glucose and other assays will be taken and stored on ice, subsequently centrifuged, and stored at -80 until further processing. Up to 7 samples will be taken from the canula (~15 ml of blood total): #1 and #2 at baseline (in duplo), #3-5 during exercise (every 10 min), #6 after 40 minutes of moderate-intensity exercise, and #7 after the final MRS-analysis when the participant has recovered from exercise.

Muscle biopsy:

Participants are given the option at the start of the trial of undergoing muscle biopsy. If the patient has given informed consent to muscle biopsy, samples will be taken before and after exercise testing protocol during one or both study visits (2 samples/run; maximal of four biopsies for the complete study). 0.25 gm. of muscle tissue will be collected using percutaneous needle biopsies from the lower third of the Vastus Lateralis muscle with a biopsy gun (Bard Monopty, Bard Biopsy Systems, USA; a sterile standard biopsy technique (SOP). Muscle biopsy will be obtained from new incisions under local anaesthesia. Tissue samples will be frozen immediately in liquid nitrogen and stored at -80 °C until further analysis. Assays include glycogen and the metabolites of the glycolytic, TCA cycles. If sufficient tissue is available, enzymatic activity of mitochondrial and cytosol proteins, muscle fibre types, amino acids, and fat stores will also be determined.

Storage of tissue samples

All samples will be frozen immediately and stored at -80°C in the laboratory for Liver, Digestive and Metabolic diseases of the department of Paediatrics at UMCG.

31P MRS

MR data gathering will be performed using a 3.0 T whole-body MR-scanner (Intera; Philips Medical Systems, Best, The Netherlands). Subjects are introduced to the scanner and exercise apparatus and instructed. MRS data gathering will be performed with a surface coil wrapped over the quadriceps muscle. Conventional anatomical MRI scans will be acquired for positioning and scanner preparation. 31P MR spectra will be acquired serially to measure dynamics in intramuscular PCr, ATP, Pi, and pH using standard 31P-MRS protocols.

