late evening snack or meal of their choice in correspondence with their individual record of maximal fasting duration, given a start time of the study at 08:00 am the following day. Patients will be allowed the same light breakfast according their normal diet before they will receive the caloric drive before the test. The breakfast will be the same for session II and III.

No adverse effects of this study are expected. Of the listed interventions that are proposed here, all but one – i.e., ingestion of the ketone caloric drink - have previously been included and approved in clinical investigations of metabolic myopathy patients by members of the investigative team in Amsterdam, Utrecht and/or Groningen: venipuncture and microbiopsy of the quadriceps muscle prior to and after exercise (protocol 04/1984 (MCADD; AMC Amsterdam); protocol **NL41313.042.12 (MCADD; UMCG)**); bouts of prolonged bicycle exercise outside and inside a MR scanner including in vivo MR spectroscopic data collection (protocol **12-211/K (VLCADD; UMC Utrecht; protocol NL41313.042.12 (MCADD; UMCG)**).

Of the interventions, only the **burden** of collecting tissue samples from the quadriceps muscle by microbiopsy is rated as moderate (as opposed to ratings of nil to minor burden for all other interventions¹). As such, this intervention will only be performed on a voluntary basis; it will not affect enrollment in the study. Muscle tissue sampling is, however, needed – and therefore desirable - to test the secondary hypothesis that NK boosts muscular mitochondrial function specifically at the level of substrate supply to the TCA cycle. Without the biopsy data, this secondary hypothesis cannot be validated. It would be highly desirable to know the outcome of that test since the information is needed to develop a proper mechanistic understanding of any therapeutic value of ketone administration in human metabolic myopathies such as fatty acid oxidation defects. On these grounds, the burden of microbiopsy is considered justifiable.

The **safety** of the nutritional drinks that will be administered and the expected acute, transient mild ketosis (concentrations of ketone bodies < 3 mM) has been thoroughly tested and documented in healthy subjects (see references 9,10). The drink has been designated as 'GRAS' (= Generally Recognized as Safe) by the Federal Drug Administration of the

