2. OBJECTIVES

1. To investigate the potential of a novel dietary substrate preparation to enhance muscle mitochondrial function in VLCADD via acute nutritional ketosis.
2. To investigate if tri-citric acid cycle substrate supply in muscle of patients with VLCADD is boosted by acute nutritional ketosis.

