11.4 Benefits and risks assessment, group relatedness

In clinical practice, many patients with VLCADD wonder to which extent they are able to exercise safely. Any means of boosting this capacity will greatly improve the quality of life and long-term health in this patient population. Acute nutritional ketosis after ingestion of a novel edible ketone ester is a very promising novel therapy towards this aim and has already been tested with positive effects in human athletes. This study will gain insight whether a sound metabolic basis exists for its therapeutic use in this patient population.

No adverse effects of this study are expected. Of the listed interventions that are proposed here, all but one – i.e., ingestion of the ketone caloric drink - have previously been included and approved in clinical investigations of metabolic myopathy patients by members of the investigativce team in Amsterdam, Utrecht and/or Groningen: venipuncture and microbiopsy of the quadriceps muscle prior to and after exercise (protocol **04/1984 (MCADD; AMC Amsterdam)**); protocol **NL41313.042.12 (MCADD; UMCG)**); bouts of prolonged bicycle exercise outside and inside a MR scanner including in vivo MR spectroscopic data collection (protocol **12-211/K (VLCADD; UMC Utrecht; protocol NL41313.042.12 (MCADD; UMCG))**). Of the interventions, only the **burden** of collecting tissue samples from the quadriceps muscle by microbiopsy is rated as moderate (as opposed to ratings of nil to minor burden for

all other interventions²). As such, this intervention will only be performed on a voluntary basis; it will not affect enrollment in the study. Muscle tissue sampling is needed to test the secondary hypothesis that NK boosts muscular mitochondrial function specifically at the level of substrate supply to the TCA cycle; therefore, the burden of micro biopsy is considered justifiable.

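### For objective 2, the unpaired Mann-Whitney test of section 10.2 ignores that two-session biopsies are paired ketone and placebo samples (optional secondary endpoint)

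*Protocol*

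**What the plan says.** Objective 2 in Protocol section 2 reads "To investigate if tri-citric acid cycle substrate supply in muscle of patients with VLCADD is boosted by acute nutritional ketosis". The data for it come from the optional biopsies, listed in section 8.1.2 as "optional: muscle levels of glycogen, lactate, 3-OH butyrate" and further metabolites before and after exercise.

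The trial is a two-way crossover. Section 3 gives the drink order as "if drink A in session II, then drink B in session III, and vice versa", and the biopsy times as "1st biopsy: 20 min after oral drink; 2nd biopsy: immediately following end of exercise bout". It lists these biopsies under sessions II and III together. Section 8.3, under muscle biopsy, says that for a consenting patient "samples will be taken before and after exercise testing protocol during one or both study visits", with two samples per session and a "maximal of four biopsies for the complete study".

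Section 10.2 promises confidence intervals, sets the significance level at 0.05 and names a two-sided Mann-Whitney test. It does not separate one endpoint from another, and section 10.3 rules out multivariate analysis. The Mann-Whitney test is therefore the only comparison stated for the biopsy data.

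**The concern.** Objective 2 is a ketone-versus-placebo question, and the crossover lets each patient serve as their own control. A patient biopsied in both sessions has a sample under each drink at each of the two sampling times. The Mann-Whitney test is for two independent groups. Applied to these data it ignores which ketone sample belongs with which placebo sample and treats the two as independent observations.

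Patients biopsied in one session are a separate matter. Both of their samples follow the same drink, so they have nothing under the other drink and no pre-drink sample. They show the change with exercise under one drink, but no within-patient drink effect.

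The protocol rests the biopsy burden, the only one it rates as moderate, on this objective. The Summary says "Without the biopsy data, this secondary hypothesis cannot be validated", and section 11.4 concludes "therefore, the burden of micro biopsy is considered justifiable". With at most six patients, the analysis should use the information that the design pays for.

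**Working it through.** The protocol gives no effect size, SD, power or precision for the biopsy endpoint, so there is no figure of its own to reproduce.

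**Inputs**
- Patients: at most 6 (section 4.1). Consenting patients give 2 biopsies per session, at most 4 in total (section 8.3).
- Unit: the between-patient SD of a muscle metabolite under one drink, set to 1 and taken as equal under both drinks.
- Correlation rho between a patient's two sessions: an assumption, shown from 0 to 0.8. The protocol gives none.
- A t interval for two independent groups stands in for the Mann-Whitney test, so that the two approaches can be compared on one scale. No period effect is modelled.

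**Half-width of the 95% interval, k patients biopsied in both sessions**
- Paired: t(0.975, k-1) × sqrt(2(1-rho)/k)
- Unpaired: t(0.975, 2k-2) × sqrt(2/k)

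Six pairs:

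| rho | Paired | Unpaired |
|---|---|---|
| 0 | 2.571 × sqrt(2/6) = 1.48 | 2.228 × sqrt(2/6) = 1.29 |
| 0.5 | 2.571 × sqrt(1/6) = 1.05 | 1.29 |
| 0.8 | 2.571 × sqrt(0.4/6) = 0.66 | 1.29 |

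The two are equal at rho = 1 - (2.228/2.571)² = 0.25. At rho 0.5 the paired interval is 18% narrower (1.05/1.29 = 0.82, using unrounded values).

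Fewer pairs, at rho 0.5:
- Five pairs: paired 2.776 × sqrt(1/5) = 1.24; unpaired 2.306 × sqrt(2/5) = 1.46. Equal at rho = 1 - (2.306/2.776)² = 0.31.
- Four pairs: paired 3.182 × sqrt(1/4) = 1.59; unpaired 2.447 × sqrt(2/4) = 1.73. Equal at rho = 1 - (2.447/3.182)² = 0.41.

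**Cost of leaving one-session patients out of the comparison**

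Take five pairs plus one single-session patient, in a generalised least squares model with known variances. At rho 0.5 the variance of the drink effect is 0.2000 for five pairs alone and 0.1917 with the single patient added. In pair equivalents, 2(1-rho)/variance = 1/0.1917 = 5.22, so the single patient adds 0.22 of a pair. The same calculation gives 0.45 at rho 0 and 0.08 at rho 0.8.

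**Smallest attainable p-value if a paired rank test were used instead**

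The smallest two-sided signed-rank p is 2/2⁶ = 0.031 with six pairs and 2/2⁵ = 0.0625 with five. Below six pairs that test cannot reach 0.05, so an interval is the more useful result.

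**Would requiring two sessions help?**

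Suppose such a rule turned six one-session volunteers into three two-session volunteers, with 12 biopsies either way. At rho 0.5, three pairs give 4.303 × sqrt(1/3) = 2.48. Six singles split 3 v 3 give 2.776 × sqrt(2/3) = 2.27. Three pairs are better only above rho = 1 - (2.776/4.303)² = 0.58.

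**The case against.** A reader might infer that section 8.3 is the fault: by allowing one session, it lets patients bear the biopsy burden without serving objective 2. The documents do not support that.
- Section 3 already lists biopsies for both sessions, and the maximum of four in 8.3 fits that.
- Biopsy is voluntary, and section 1 reports that the protocol's intensity was the main reason for refusal. Accepting two biopsies where the alternative may be none is defensible.
- At the same assumed correlation of 0.5, the scenario above favours six one-session volunteers over three two-session ones.
- One-session samples are not worthless. Section 3 also gives the biopsies a descriptive purpose (fibre type, mitochondrial and capillary density), and they carry some between-patient information.

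These points stand, and they are why 8.3 is not treated as an error.

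Against the point on 10.2 it can be said that analysis detail belongs in a statistical analysis plan, which may exist. That would answer a silence, but 10.2 states a test, and the test does not fit paired data. The reporting of one-session samples could be left to that plan; it is raised here only because it follows from the change.

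It can also be said that a rank test suits six patients better than a t interval. It is true that the t interval assumes roughly normal differences, which six values cannot confirm. But this argues for care with the scale of measurement. It does not justify treating paired samples as independent.

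Finally, the gain in precision is not assured. At low correlation the unpaired interval is narrower, and the break-even rises as pairs become fewer.

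**Conclusion.** The point holds for the analysis. For objective 2, section 10.2 applies a test for independent groups to samples that are paired by design whenever a patient is biopsied in both sessions. With six pairs and an assumed correlation of 0.5, using the pairing reduces the half-width from 1.29 to 1.05 SD. The benefit reverses below a correlation of about 0.25 with six pairs, or about 0.41 with four. These figures rest on equal variances, a t interval in place of the rank test, and a correlation that the protocol does not supply.

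The consequence is limited to an optional secondary endpoint. Although 10.2 names one test for everything, this point makes no claim about the primary MRS endpoints. It also does not say that one-session biopsy is wrong or that objective 2 cannot be addressed.

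**What to change.** Add to section 10.2: *Objective 2 is estimated from within-patient ketone-minus-placebo differences, with a t-based 95% confidence interval. Patients biopsied in one session only are reported descriptively.* This replaces the Mann-Whitney test for this endpoint and fits the section's existing promise of confidence intervals.

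The cost is a short addition to the text. The downside is that one-session samples leave the formal comparison. That is a small loss: 0.22 of a pair each beside five pairs at correlation 0.5, with a range of 0.45 to 0.08 for correlations of 0 to 0.8.

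Optionally, 8.3 could be worded as *both sessions II and III where the patient agrees; one session may be declined*. This is a clarification and not a correction: it leaves the allowed sampling and the maximum of four biopsies unchanged, and a firmer expectation of two sessions may cost volunteers.
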